10.4.2 Statistical Hypothesis, Model, and Method of Analysis

No statistical test of hypotheses will be performed in this study.

The primary analysis for this study is to estimate the PFS rate over time and its 95% CI by the method of Kaplan-Meier for:

1. All patients;
2. First-line patients (receiving RAD001 as their first treatment);
3. Second-line patients (patients who received cytokine therapy as first-line therapy).

Progression-free survival curves (graphing the PFS rate over time) will be displayed, overall and by strata, according to the Kaplan-Meier product-limit method. The PFS rate over time will also be tabulated. The resulting median PFS time will be given with 95% CIs.

The primary analysis will be performed on the Full Analysis Set (FAS). Consolidated summary results obtained from the local radiological review will be used for this analysis.

10.4.3 Handling of Missing Values/Censoring/Discontinuations

By default, if disease progression or death is documented after one single missing tumor assessment, the actual event date of disease progression/death will be used for the PFS event date. If disease progression is documented after two or more missing tumor assessments, the PFS time of these patients will be censored at the date of the last tumor assessment, with overall lesion response of CR, PR, or SD.

Additionally, sensitivity analyses will be performed where:

1. The actual event date of disease progression/death will be used for the PFS event date, irrespective of whether it is preceded by missing tumor assessments;
2. In case of a documented progression/death after one or more missing tumor assessments, disease progression is considered to have occurred at the next scheduled tumor assessment after the date of the last tumor assessment with overall lesion response of CR, PR, or SD.

10.4.4 Supportive Analyses

The primary analysis will also be performed on all available events (progressions) as per local radiological review, as a supportive, secondary analysis.

All analyses will be fully described and document in the statistical analysis plan (SAP).

10.5 Secondary Objectives

10.5.1 Secondary Efficacy Evaluation

The analyses of all secondary efficacy endpoints will be performed on the FAS.

10.5.1.1 Disease Control Rate (SD + PR + CR)

The disease control rate will be based on the data as per local radiological review, following the RECIST criteria. The disease control rate is defined as the proportion of patients with CR,

PR, or SD. The disease control rate (CR + PR + SD) will be summarized in terms of percentage with 95% CIs.

10.5.1.2 Objective Response Rate and Duration

The overall tumor response will be based on the data as per local radiological review, following RECIST criteria. The ORR is defined as the proportion of patients with CR or PR. The ORR (CR + PR) will be summarized in terms of percentage with 95% CIs.

The duration of overall response (CR or PR) will also be calculated, and is defined as the time from the first occurrence of PR or CR (as per local radiological review) until the date of the first documented disease progression or death due to underlying cancer. If a patient has not had an event, or when he/she receives any further anticancer therapy, duration of overall response is censored at the date of the last adequate tumor assessment. In case of missing data, the same rules will be applied as for PFS (see [Section 10.4.3](#)).

Duration-of-response curves (graphing the proportion of patients remaining free from progression and death due to cancer) will be displayed, overall and by strata, according to the Kaplan-Meier product-limit method, for those patients who had an overall response. This proportion over time will also be tabulated. The resulting median duration of response will be given with 95% CIs.

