10.4.1 Variable: Progression-Free Survival

The primary endpoint of this study, PFS, is defined as the time from the date of the start of RAD001 treatment to the date of the first documented disease progression or death due to any cause.

A patient who has not progressed or died at the date of the analysis cut-off, or when he/she receives any further anticancer therapy, would have his/her PFS censored at the time of the last tumor assessment, before the first of the cut-off date or the anticancer therapy date.

For the primary analysis, PFS will be based on the review by the local radiologist who, together with the investigator, will determine the local assessment of response and progression according to the RECIST criteria.

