- To be assigned a status of PR or CR, changes in tumor measurements must be confirmed by repeat assessments that should be performed no less than 4 weeks after the criteria for response are first met. Longer intervals as determined by the study protocol may also be appropriate.

- In the case of SD, follow-up measurements must have met the SD criteria at least once after study entry at a minimum interval (in general, not less than 6-8 weeks) that is defined in the study protocol.

Duration of overall response

- The duration of overall response is measured from the time measurement criteria are met for CR or PR (whichever status is recorded first) until the first date that recurrence or PD is objectively documented, taking as reference for PD the smallest measurements recorded since the treatment started.

Duration of stable disease

- SD is measured from the start of the treatment until the criteria for disease progression are met, taking as reference the smallest measurements recorded since the treatment started.
- The clinical relevance of the duration of SD varies for different tumor types and grades. Therefore, it is highly recommended that the protocol specify the minimal time interval required between two measurements for determination of SD. This time interval should take into account the expected clinical benefit that such a status may bring to the population under study.

Response review

- For studies where the response rate is the primary endpoint it is strongly recommended that all responses be reviewed by an expert(s) independent of the study at the study's completion. Simultaneous review of the patients' files and radiological images is the best approach.

Reporting of results

- All patients included in the study must be assessed for response to treatment, even if there are major protocol treatment deviations or if they are ineligible. Each patient will be assigned one of the following categories: 1) CR, 2) PR, 3) SD, 4) PD, 5) early death from malignant disease, 6) early death from toxicity, 7) early death because of other cause, or 9) unknown (not assessable, insufficient data).

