The duration of response (CR or PR) is defined as the time from the first occurrence of PR or CR (as per the local radiological review) until the date of the first documented disease progression or death due to underlying cancer. If a patient has not had an event, duration of response is censored at the date of last adequate tumor assessment prior to starting new anticancer therapy.

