7.6 Time to Event Analysis

At each visit where tumor assessment is performed the CRF will capture the RECIST assessment of tumor response according to local radiological review. If disease progression occurs then the End of Treatment pages of the CRF should be completed.

The patient's status at the end of study will be summarized with patients being classed as either alive, dead or lost to follow-up and either having had a relapse/recurrence or not. Further, if the patient has died it will be summarized whether death was due to study indication or not. These summaries will be performed on the ITT population.

The time to event variables are defined in Section 7.2.1.

No statistical test of hypotheses will be performed in this study. PFS rate and 95% confidence intervals will be presented graphically and tabulated, overall and by strata, using the Kaplan-Meier product-limit method. The resulting median PFS will be presented along with 95% CIs. These analyses will be performed on the ITT population.

The analysis of PFS will be repeated for the sensitivity analyses described in Section 7.2.3 and also for Duration of Response.

For Overall Survival the Kaplan-Meier curve will be displayed and the median, 25th and 75th percentile of the Kaplan-Meier estimate will be reported for the ITT population.

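### Duration of response counts only cancer deaths, so other deaths among responders are censored; if any occur, the Kaplan-Meier estimate is biased upward

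*Protocol*

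**What the plan says.** Protocol 10.5.1.2 measures duration of response from first PR or CR to the "date of the first documented disease progression or death due to underlying cancer". Without an event, "duration of overall response is censored at the date of the last adequate tumor assessment". The same section describes the plotted curve as the "proportion of patients remaining free from progression and death due to cancer".

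SAP 7.2.1 agrees. Duration runs "until the date of the first documented disease progression or death due to underlying cancer", and "If a patient has not had an event, duration of response is censored at the date of last adequate tumor assessment" before any new anticancer therapy.

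The other time-to-event endpoints use a different death rule. PFS (protocol 10.4.1) ends at the "first documented disease progression or death due to any cause", and overall survival (protocol 10.5.1.3, SAP 7.2.1) also counts every death.

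Two further places bear on the point:

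- The SAP programming note after Table 14.6-2.3 tells the programmer to reuse that PFS template for Table 14.6-2.5, the duration-of-response table. The template's footnote defines an event as progression or death in the period, with no restriction on cause.
- The RECIST reference in protocol section 14 measures duration "until the first date that recurrence or PD is objectively documented" and does not mention death.

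Neither document plans an any-cause version of duration of response or a competing-risk analysis.

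**The concern.** Kaplan-Meier assumes that a censored patient has the same prospects as those still followed. A responder who has died has no further response to contribute, so censoring that patient is informative. The estimate then describes a setting in which non-cancer deaths do not occur, and it can only be read as duration of response in the treated patients if there were none.

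The bias favours the drug, and in a single-arm study no control arm shares it. The rule also makes the event depend on attributed cause of death, for which neither document describes adjudication. One death can be an event in PFS and a censored observation in duration of response. The reused footnote would tell readers of Table 14.6-2.5 that all deaths are events when the definition says otherwise.

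**Working it through.** **What the plan gives.** The documents state no expected median duration of response, number of responders or non-cancer death rate, so there is no planned figure for this endpoint to reproduce. The plan's only precision calculation concerns the 10-month PFS rate. It reproduces: 2 × 1.96 × √(0.25/55) = 0.264 (stated as about 0.27) and 2 × 1.96 × √(0.25/110) = 0.187 (stated as about 0.19). It does not involve duration of response.

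**How one death is classified.** Take a responder who dies of a non-cancer cause before progression and before any new anticancer therapy.

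| Endpoint | Treatment of this death |
|---|---|
| Overall survival | Event at death |
| PFS | Event at death, normally |
| Duration of response, both texts | Censored at last adequate scan |
| Table 14.6-2.5, reused footnote | Labelled as an event |

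Scans are 12 weeks apart after week 8, so censoring can fall up to about 12 weeks before the death.

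**Closed form.** Let h1 be the hazard of progression or cancer death and h2 the hazard of non-cancer death, both constant and independent.

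- Any-cause median = ln 2/(h1 + h2).
- Median with non-cancer deaths censored = ln 2/h1.
- Ratio = (h1 + h2)/h1 = 1/(1 − f), where f = h2/(h1 + h2).

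**Simulation.** The assumptions are 35 responders (the 32% response rate in protocol 1.2.3.4 applied to 110 patients gives 35.2), a true any-cause median of 9 months, scans every 12 weeks, progression dated at the next scan, administrative censoring 10 to 28 months after response, and 3,000 replicates per setting. Means are over replicates in which the median was reached.

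| f (assumed) | 1/(1 − f) | 35 × f | Mean median, any-cause (months) | Mean median, plan's rule (months) | Plan's median higher |
|---|---|---|---|---|---|
| 0% | 1.00 | 0 | 10.6 | 10.6 | 0% |
| 5% | 1.05 | 1.75 | 10.5 | 11.0 | 20% |
| 10% | 1.11 | 3.5 | 10.5 | 11.5 | 36% |
| 20% | 1.25 | 7 | 10.3 | 12.7 | 66% |
| 30% | 1.43 | 10.5 | 10.2 | 14.1 | 87% |

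The ratios of mean medians at 5% and 10% (11.0/10.5 = 1.05; 11.5/10.5 = 1.10) agree with the closed form. The plan's median was lower in fewer than 0.1% of replicates and otherwise equal. Because progressions fall on a 12-week grid, the middle value of the simulated medians was 11.04 months under both rules at f = 5%, 10% and 20%. With 10 or 20 responders the direction was the same.

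**The case against.** The strongest defence is that the definition is deliberate and disclosed. The protocol and SAP texts agree, and the protocol says openly what the curve shows. The appended RECIST reference ends duration at recurrence or progression without mentioning death, so the plan already counts more events than that reference does. No hypothesis is tested, and the endpoint is descriptive and limited to responders. All of this stands. It means that the definitions in the two texts do not contradict each other; the mismatch is with the SAP's own table footnote and with the death rule used for PFS and overall survival.

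A reader might infer that fatal toxicity among responders is hidden. The documents do not support that:

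- These deaths are events in overall survival and normally in PFS.
- Deaths reportable as SAEs are listed and tabulated (protocol 10.5.2, SAP 8.1).
- Under SAP 7.6, "if the patient has died it will be summarized whether death was due to study indication or not", and Table 14.6-1.1 splits deaths from other reasons by prior recurrence.
- Listing 16.6-1.4 gives the principal cause of death. Listing 16.6-1.5 shows objective response, duration, censoring and date of death or last contact for each patient.

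A reader might also infer that such a patient is carried forward as still responding. That is not the rule: follow-up stops at the last adequate scan, and the fault is informative censoring.

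Finally, the bias is conditional. With no non-cancer deaths before progression the two definitions give identical results, and the documents offer no rate. The protocol synopsis describes pneumonitis with this drug class as usually mild and reversible, so a large f cannot be presumed. That limits the likely size but does not make censoring a death appropriate.

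**Conclusion.** The point holds as a minor correction. Both documents censor non-cancer deaths among responders, and this biases the Kaplan-Meier duration of response upward if such deaths occur. Under constant independent hazards the median is inflated by about 5% at f = 5% and 11% at f = 10%. Both values of f are assumptions. With only a few such deaths the reported median may stay on the same scan date.

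The documents do not support saying outright that the median is overstated: they show the direction of a possible bias, not that it will arise or how large it will be. Primary PFS, response rate, overall survival and the sample size are unaffected. Comparability with PFS is only partly at issue, since duration of response starts at response and covers responders only; what can be aligned is the death rule.

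**What to change.** 1. In protocol 10.5.1.2 and SAP 7.2.1, define the event as first documented progression or death due to any cause, as for PFS.
2. In protocol 10.5.1.2, change the description of the curve to match; otherwise the section would contradict its own definition.
3. Confirm that the footnote of Table 14.6-2.5 agrees with the definition. The reused PFS wording would then be correct as regards deaths.
4. If the cancer-death version is still wanted, report it as a labelled supplementary line.

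The cost is small. Date and cause of death are already collected, so no new data are needed. The protocol text would change by amendment under section 11.6. The downside is that the median duration of response may be slightly shorter.

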10.5.1.3 Overall Survival

Overall survival is defined as the time from date of start of treatment to date of death due to any cause. If a patient is not known to have died, survival will be censored at the date of last contact. Overall survival will be analyzed for the FAS. The Kaplan Meier curve will be displayed. Median, 25th and 75th percentile of the Kaplan Meier estimator along with their 95% confidence intervals will be reported.

10.5.2 Safety Evaluation

For all safety analyses, the Safety population will be used. The assessment of safety will be based mainly on the frequency of AEs and on the number of laboratory values that fall outside of pre-determined ranges. Other safety data (i.e., ECG, vital signs) will be considered as appropriate.

For all safety analyses, the safety population will be used. The assessment of safety will be based mainly on the frequency of AEs and on the number of laboratory values that fall outside of pre-determined ranges. Other safety data (i.e., electrocardiogram, vital signs) will be considered as appropriate.

Adverse events will be summarized by presenting the number and percentage of patients having any AE, having an AE in each body system and having each individual AE. Any other information collected (e.g., CTC grades or relatedness to study drug) will be listed as appropriate. In addition, the incidence of pneumonitis AEs will be summarized by preferred term.

Deaths reportable as SAEs and non-fatal SAEs will be listed by patient and tabulated by the type of AE.

Laboratory data will be summarized by presenting shift tables using CTC grades (screening to most extreme post-screening value), by presenting summary statistics of raw data and change from baseline values (means, medians, standard deviations) and by the flagging of CTC grades in data listings.

Data from other tests (e.g., electrocardiogram or vital signs) will be listed and any other information collected will be listed as appropriate.

10.5.3 Tolerability

Frequency and severity of all treatment-emergent AEs will be listed.

10.5.4 Resource Utilization

No resource utilization will be specifically collected in this study.

10.5.5 Patient-Reported Outcomes

No patient-reported outcomes are planned.

10.5.6 Pharmacokinetics

Not applicable.

10.5.7 Biomarkers

Not applicable.

10.6 Interim Analysis

No interim analysis is planned for this study.

10.7 Sample Size Calculation

By way of background, Hudes et al. (2006), for first-line poor-prognosis metastatic RCC patients, estimated at 3.8 months a PFS rate of 50% for temsirolimus treatment. Amato, et al. 2008 (draft manuscript), for mostly second-line RCC patients, observed at 11.2 months a PFS rate of 50% for everolimus (RAD001) treatment. How patients are selected (i.e., whether the selected patients are poor-prognosis patients or patients are selected irrespective of prognosis) may have a large impact on the observed median PFS.

The sample size for this study will be determined with reference to estimating a CI for the PFS rate at 10 months, assuming (for simplicity) the use of the normal approximation to the binomial distribution and assuming that a CI for a proportion is based on this normal approximation. To be able to estimate a 95% CI for the PFS rate, centered at 0.50, and having an expected total interval width of approximately 0.27, requires a sample size of 55 patients in each cohort (first- and second-line). With 95% confidence, the expected total interval width is approximately 0.19 for all 110 patients (both cohorts combined).

Some alternative sample size calculations, using different assumptions about the desired expected CI width, are as shown in Table 8.

Table 8 Number of Patients Required per Cohort Depending on Desired Width of

Confidence Interval (CI) for the 10-Month Progression-Free Survival Proportion

Expected CI Width for One Cohort	Number of Patients Required Per Cohort	Total Required Number of Patients	Expected CI Width for all Patients Combined
0.2	97	194	0.14
0.25	62	124	0.18
0.3	43	86	0.21
0.35	32	64	0.24
0.4	25	50	0.28

10.8 Power for Analysis of Critical Secondary Variables

Not applicable.

11 Administrative Procedures

11.2 Regulatory and Ethical Compliance

This clinical study was designed and shall be implemented and reported in accordance with the protocol, the International Conference on Harmonisation (ICH) Harmonised Tripartite Guidelines for Good Clinical Practice (GCP), with applicable local regulations (including European Directive 2001/20/EC and US Code of Federal Regulations Title 21), and with the ethical principles laid down in the Declaration of Helsinki.

11.3 Responsibilities of the Investigator and IRB/IEC/REB

The protocol and the proposed informed consent form must be reviewed and approved by a properly constituted Institutional Review Board (IRB)/Independent Ethics Committee (IEC)/Research Ethics Board (REB) before study initiation. A signed and dated statement that the protocol and informed consent have been approved by the IRB/IEC/REB must be given to Novartis before study initiation. Prior to study start, the investigator is required to sign a protocol signature page confirming his/her agreement to conduct the study in accordance with these documents and all of the instructions and procedures found in this protocol and to give access to all relevant data and records to Novartis monitors, auditors, Novartis Clinical Quality Assurance representatives, designated agents of Novartis, IRBs/IECs/REBs, and regulatory authorities as required.

11.4 Informed Consent

Eligible patients may only be included in the study after providing written (witnessed, where required by law or regulation), IRB/IEC/REB-approved informed consent, or, if incapable of doing so, after such consent has been provided by a legally acceptable representative of the patient. In cases where the patient's representative gives consent, the patient should be informed about the study to the extent possible given his/her understanding. If the patient is capable of doing so, he/she should indicate assent by personally signing and dating the written informed consent document or a separate assent form. Informed consent must be obtained before conducting any study-specific procedures (i.e., all of the procedures described in the protocol). The process of obtaining informed consent should be documented in the patient source documents.

Novartis will provide to investigators in a separate document a proposed informed consent form that complies with the ICH GCP guidelines and regulatory requirements and is considered appropriate for this study. Any changes to the proposed consent form suggested by the investigator must be agreed to by Novartis before submission to the IRB/IEC/REB, and a copy of the approved version must be provided to the Novartis monitor after IRB/IEC/REB approval.

Females of childbearing potential should be informed that taking the study drug may involve unknown risks to the fetus if pregnancy were to occur during the study and agree that in order to participate in the study they must adhere to the contraception requirement for the duration of the study. If there is any question that the patient will not reliably comply, they should not be entered in the study.

